#### **CTDs, Fibromyalgia, Cancer, Neurological Diseases and Suicide**

*The incidence of CTDs (by type), fibromyalgia, cancer (by type), neurological disease (by type), and suicide will each be estimated as the ratio of the number of new cases to the number of person-years of exposure (i.e., observed person-years with silicone breast implants) for MemoryGel participants only. Ninety-five percent confidence intervals will be computed. For CTDs, the incidences of scleroderma, lupus, rheumatoid arthritis, Sjögren's Disease, fibromyalgia, and other CTDs will each be estimated. For cancer, the incidences of breast, brain, lung, and other cancers will each be estimated. For neurological diseases, the incidences of MS, myositis, and other neurological diseases will each be*

*estimated. In addition, Mentor will examine the prevalence of depression and anxiety. Ninety-five percent confidence intervals will be computed.*

*The relative risk for women with MemoryGel implants as compared to national norms will be estimated, standardizing for age, race, and other relevant characteristics, when appropriate. The relative risk will be tested for significance based on a one-sided test conducted at the 0.05 level of significance. Ninety-five percent confidence intervals will also be computed. The sources for the comparison data will include Mayes et al. (2003), and may also include, as appropriate, relevant historical controls such as Brinton et al. (2000, 2001a and b, 2004, and 2006), Hennekens et al. (1996), Deapen et al. 1997, Surveillance Epidemiology and End Results (SEER), National Violent Death Reporting System, U.S. Census data (2002), and/or other reliable and relevant sources, including new sources that may become available during the course of this study. The sources for the comparison data for fibromyalgia will include Brinton et al. 2004, the saline control participants, and/or other reliable and relevant sources, including new sources that may become available during the course of this study.*

*The baseline questionnaire, as well as the follow-up questionnaire, includes recommendations to all participants to see a rheumatologist or neurologist when the participant indicates she is experiencing certain combinations of signs and symptoms. At baseline, a participant will be advised to see a rheumatologist or neurologist if she identifies certain trigger signs and symptoms as specified in the questionnaire. If a participant does not choose to wait until her specialist evaluation before receiving implants, like all participants, she will be followed for the duration of the study, regardless of what the finding is.*

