## 1.0 INTRODUCTION

On 17 Nov 2006, the U.S. Food and Drug Administration (FDA) approved Mentor's MemoryGel® silicone gel-filled breast implants for use in women who are undergoing primary or revisional breast augmentation and primary or revisional breast reconstruction surgery. The approval was conditional on Mentor conducting a 10-year study designed to collect long-term experience in U.S. women with MemoryGel implants. The MemoryGel Postapproval Study (MemoryGel PAS) is intended to satisfy one element of FDA's postapproval requirements.

As a condition to gaining access to MemoryGel products, physicians were required to sign up for the MemoryGel Gel-Filled Breast implants Post Approval study, and were asked to actively encourage 41,900 women to participate in the 10-year study. In addition, the study included 1,000 women who were undergoing breast implantation with saline breast implants to serve as concurrent controls for assessing rheumatologic and neurologic signs and symptoms.

Approximately 1,700 centers participated in the study and enrollment included 41,451 MemoryGel participants and 1039 saline participants. Study enrollment has been closed since 15 Oct 2008. As of the last annual study report (dated Nov 2013), the follow-up rates through six years were 21.8% for MemoryGel participants and 15.0% for saline participants.

Due in part to the low follow-up rate, which may limit interpretation of the data, FDA in collaboration with the American Society of Plastic Surgeons (ASPS), breast implant manufacturers, and patient representatives have been investigating innovative approaches to collect long-term data on silicone gel breast implants. As part of these efforts, recently, FDA has agreed to changes in the postapproval commitments for the MemoryGel silicone gel-filled breast implants that include changes to MemoryGel PAS. These changes are described in this amended protocol.

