## 4.0 PARTICIPANT POPULATION

Study enrollment has been closed since 15 Oct 2008 and no new study participants will be enrolled. Approximately 1,700 centers participated in the study and enrollment included 41,451 MemoryGel participants and 1,039 saline participants. As of the last annual study report (dated Nov 2013), the follow-up rates through six years were 21.8% for MemoryGel participants and 15.0% for saline participants.

The postapproval study was originally designed with the following eligibility criteria:

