## 11.2 Sample Size Determination

Study enrollment has been closed since 15 Oct 2008 and no new study participants will be enrolled.

The sample size for the postapproval study originally was determined in the following manner:

*It is assumed that it is required to have 80% power to be able to detect as statistically significant a relative risk of 2.0 for adverse events that occur, without implants, with a frequency of 2.85 per 100,000. This figure is based on the incidence of scleroderma as reported by Mayes et al. (2003). It is assumed this would be based on a one-sided test conducted at the  $\alpha = 0.05$  level of significance. Based on these specifications, it was determined that approximately 338,000 person-years would be required.*

*Patients are to be followed for 10 years. For purposes of sample size calculation, assuming a follow-up rate of 65% at 10 years and a linear loss to follow-up, there would be an average of 8.075 person-years per participant. Thus, in order to obtain the 338,000 person-years, a total of 41,900 MemoryGel participants would be required.*

*The concurrent control sample size was selected in order to be able to detect a relative risk of 2.0 for MemoryGel participants as compared to control participants, for rheumatologic and neurologic signs and symptoms with a prevalence of approximately 2% among MemoryGel participants. It is assumed this would be based on a one-sided test conducted at the 0.05 level of significance with a power of 80%. Similar combined rheumatologic categories of signs and symptoms from Mentor's existing Core Study of these silicone gel implants all have estimated prevalence of at least 2% after year 2. These data will be analyzed by first computing, for each participant, the proportion of time points in which the participant reports the sign or symptom as being prevalent and then calculating the mean of these participant-level proportions across participants within each group. For purposes of sample size calculation, it is assumed that these means will be compared using a simple test based on the normal approximation.*

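### Disease incidence and relative risk are pooled over all person-years with no split by time since implantation, so the Amendment 1 estimates lean towards the early years and would dilute a late excess

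*Combined protocol and SAP*

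**What the plan says.** Section 1.0 makes the approval conditional on a "10-year study designed to collect long-term experience in U.S. women with MemoryGel implants".

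In Section 11.1 (CTDs, Fibromyalgia, Cancer, Neurological Diseases and Suicide), each incidence is "estimated as the ratio of the number of new cases to the number of person-years of exposure", and exposure is glossed as "i.e., observed person-years with silicone breast implants) for MemoryGel participants only". The comparison with national norms is made "standardizing for age, race, and other relevant characteristics, when appropriate". One test per disease follows: "The relative risk will be tested for significance based on a one-sided test conducted at the 0.05 level of significance". Time since implantation is not named, and no lag or interval is specified. Estimates over time (Kaplan-Meier) are planned only for complications and reoperations, rupture and MRI.

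This text comes from the original protocol, but Section 11.1 also states that the final report on the Amendment 1 phase will use the original analysis. Sections 1.0 and 3.0 end the annual questionnaires, with the study in year 7, so that report is the last disease analysis under this protocol.

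On retention, Section 11.2 sized the study for "80% power to be able to detect as statistically significant a relative risk of 2.0", "assuming a follow-up rate of 65% at 10 years and a linear loss to follow-up". Section 4.0 reports that "the follow-up rates through six years were 21.8% for MemoryGel participants and 15.0% for saline participants". The documents give no year-by-year retention and no accrued person-years.

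**The concern.** A pooled rate counts a person-year six months after surgery the same as one six years after. That is harmless if the relative risk is constant. If an excess appears only after some years, the pooled relative risk averages it with the earlier period in which there was none. The more the person-time is bunched in the early years, the closer the pooled value sits to 1.

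This is separate from the loss of total person-years. Fewer person-years widen the interval; a change in their mix moves the estimate itself. A reader who meets a pooled relative risk near 1 in a report from a ten-year study may take it as long-term reassurance, and nothing in the planned output would show how much late person-time stands behind it.

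**Working it through.** **The plan's own figures.** Counting retention at the end of each year, the sum over k = 1 to 10 of (1 - 0.035k) is 8.075 person-years per woman, as stated in Section 11.2. 338,000 / 8.075 = 41,858, stated as 41,900. With 2.85 per 100,000 read as per person-year, 338,000 person-years give 9.63 expected cases. An exact one-sided Poisson test with critical count 16 then has a level of 0.037 and power of 80.2% at a relative risk of 2.0. The plan reproduces.

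**Inputs for the check.** Planned retention is S(t) = 1 - 0.035t (Section 11.2). Reported retention is S(6) = 0.218 (Sections 1.0 and 4.0), taken as continued retention with person-time ending at loss. MemoryGel enrollment is 41,451. The last year of disease data is not stated per woman, so 6, 7 and 8 are tried.

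**Formula.** The share of person-years in a band is the integral of S(t) over the band divided by its integral from 0 to the end of data.

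| Retention curve | Data end (year) | Person-years per woman | Years 0-2 | After year 5 |
|---|---|---|---|---|
| Planned, linear | 10 | 8.25 | 23.4% | 44.7% |
| Planned, cut | 6 | 5.37 | 35.9% | 15.0% |
| Linear to 21.8% at year 6 | 6 | 3.65 | 47.6% | 7.7% |
| same | 7 | 3.81 | 45.7% | 11.5% |
| same | 8 | 3.84 | 45.3% | 12.1% |
| Exponential to 21.8% at year 6 | 6 | 3.08 | 50.9% | 8.1% |
| same | 7 | 3.27 | 47.9% | 13.5% |
| same | 8 | 3.42 | 45.8% | 17.2% |
| All loss in year 1, then flat | 6 | 1.70 | 48.7% | 12.8% |
| same | 7 | 1.92 | 43.1% | 22.7% |
| same | 8 | 2.14 | 38.7% | 30.6% |

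(The continuous integral gives 8.25 for the plan instead of 8.075; the share in years 0-2 is 23.5% on the end-of-year count, so the difference does not matter.)

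These three curves span 39-51% in years 0-2 and 8-31% after year 5. If the loss is instead spread over the first two or three years and then stops, the share in years 0-2 reaches 58-60% with data to year 6. Any non-increasing curve through 21.8% at year 6, with data to year 6, must lie between 33% and 70%.

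**Loss or cut-off?** Take the linear curve to year 6. Years 0-2 rise from 23.4% to 47.6%, or 24.2 points, of which 35.9 - 23.4 = 12.5 come from stopping at year 6 alone. After year 5 the share falls from 44.7% to 7.7%, or 37.0 points, of which 44.7 - 15.0 = 29.7 come from stopping. So about half of the early shift and about 80% of the late shift is the cut-off; the rest is loss.

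**Dilution.** If the reference rate is constant and the true relative risk is 1 before onset and 2.0 after, the pooled value is 1 + (share of person-years after onset).

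| Onset of excess | Linear, to year 6 | Exponential, to year 6 | Planned, to year 6 | Planned, to year 10 |
|---|---|---|---|---|
| Year 2 | 1.52 | 1.49 | 1.64 | 1.77 |
| Year 5 | 1.08 | 1.08 | 1.15 | 1.45 |

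The most favorable row of the first table (loss in year 1, data to year 8) gives 1.61 and 1.31.

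**What late bands can hold.** With linear loss to year 6, 41,451 x 3.654 = about 151,500 person-years. At 2.85 per 100,000 that is 4.3 expected scleroderma cases in total, and 0.0775 x 4.32 = about 0.3 after year 5.

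**The case against.** The strongest reply has four parts.

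1. **The stated question.** Table 1 asks for types and rates of CTD and cancer; only local complications are asked over time. A pooled rate answers that question, the study was sized on pooled person-years, and Section 1.0 already concedes that low follow-up may limit interpretation. This stands as a reason to keep the pooled estimate. It does not show a reader where the person-time lies, and the approval condition concerned long-term experience.

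2. **The retention input is undefined.** The six-year rate could be questionnaire completion rather than continued retention. Under Section 14.0 a woman was discontinued for non-compliance only after three years with neither a questionnaire nor a surgeon's form, so missing year 6 is not the same as being lost. Suicide is also ascertained through the Social Security Death Index (Table 1, footnote 7), so questionnaire loss need not end that person-time. This stands, and it is why the shares are ranges.

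3. **No latency is given.** The documents state no onset time for any disease. The steps at year 2 and year 5 are illustrations of dilution, not evidence of harm.

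4. **Late bands would be nearly empty for rare disease.** True for scleroderma, and the remedy has to allow for it.

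A reader might go further and infer that the relative risks describe early risk only, or that the reported loss alone turned a long-term study into a short-term one. The documents support neither. On every curve in the first table, roughly half or more of the person-years fall after year 2, so the estimate mixes both periods. Setting a curve that ends at year 6 against a plan that runs to year 10 also charges to loss what is partly the end of data collection.

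**Conclusion.** The point holds in a limited form. The pooled relative risk in the Amendment 1 report will be weighted towards the early years, with little or no information on years 7-10, and the plan provides no output that shows this. Years 0-2 carry about 39-51% of person-years against 23% in the ten-year plan; the years after year 5 carry about 8-31% against 45%. Loss and the end of disease data collection both contribute. An excess that began late would be diluted, to about 1.5 for onset at year 2 and 1.08 for onset at year 5 under linear or exponential loss to year 6.

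These sizes rest on four assumptions: that 21.8% is continued retention, that person-time ends at loss, the shape of the loss curve, and data ending between years 6 and 8. The dilution figures also assume a constant reference rate and a step in risk. The direction against the ten-year plan is the same on every curve tabulated; the exact share needs the database. This is a worthwhile, inexpensive improvement to the report and does not make the pooled estimate invalid.

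**What to change.** Keep the pooled estimate. In the Amendment 1 final report:

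- Add a table, per disease, of observed person-years, observed cases and expected cases by time since implantation, for example 0-2, 2-5 and over 5 years. State how person-time is counted for women who skip questionnaires and return.
- Give band-specific relative risks with intervals where expected counts allow, for example all cancers and all CTDs.
- Add a sensitivity relative risk for cancer and CTD that leaves out the first 2 years.
- For suicide, note that the death index may extend person-time beyond questionnaire loss.
- Limit statements on long-term risk to what the late bands support.

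The cost is splitting person-time already in the database, plus one table. The downside is wide intervals in the late bands and near-empty bands for rare diseases such as scleroderma. The band limits and the 2-year lag are suggestions; they should be fixed before the results are seen.

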### 3.0 DESIGN

This protocol amendment includes participant follow-up only. Study enrollment has been closed since 15 Oct 2008 and no new study participants will be enrolled. Data collection will only take place if a participant requires a secondary procedure/reoperation. There are no longer requirements for scheduled office visits or annual participant questionnaires. The study is currently in year 7 and follow-up will continue through 10 years or until the National Breast Implant Registry opens for data collection, whichever occurs first.

As in the original protocol, there will be no concurrent controls needed as a source of comparison for secondary procedures/reoperations (see local complications category in original study design Tables 1 and 2). Thus, saline implant participants will not have data collected under this amended protocol.

Mentor will employ third party study entities that will be responsible for the following: (1) collecting data from surgeons; (2) entering data into and administering the study database; (3) generating follow-up reports as well as datasets; (4) meeting with Mentor on a regular basis; and (5) analyzing the study data. Mentor will be responsible for: (1) IRB approval; (2) monitoring third party entities; (3) analyzing the study data; and (4) periodic reporting to FDA.

The postapproval study was originally designed as follows:

*MemoryGel™ PAS uses a current cohort design of the first 41,900 women receiving Mentor's MemoryGel implants, with 10 years of follow-up. It will include augmentation, reconstruction, and revision patients, each in their naturally occurring proportions at participating study sites.*

*For the purpose of assessing rheumatological and neurological signs and symptoms, there also will be 1,000 saline breast implant patients from the participating surgeons' practices who will serve as concurrent controls. Concurrent control participants will be enrolled by approximately 30 physicians who routinely use saline implants. These investigative sites will be selected with the objective of obtaining the desired number of controls in an appropriate time frame, e.g. roughly the same time frame as the recruitment of MemoryGel subjects. These sites are to enroll all saline subjects meeting the specified eligibility criteria until 1,000 controls are recruited into this study.*

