 The sources for the comparison data may include, as appropriate, relevant historical controls such as the Centers for Disease Control's Pregnancy Risk Assessment Monitoring System (PRAMS), Center for Disease Control's Vital and Health Statistics, National Birth Defects Prevention Network, the California Birth Defects Monitoring Registry, the National Institutes of Health's (NIH's) First and Second Trimester Evaluation of Risk for Aneuploidy (FASTER) Trial, National Health and Nutrition Examination Survey (NHANES), and /or other reliable and relevant sources, including new sources that may become available during the course of this postapproval study, such as the National Children's Study.

 The sources for the comparison data may include, as appropriate, relevant historical controls such as Centers for Disease Control, National Survey of Family Growth, Centers for Disease Control Vital and Health Statistics, National Birth Defects Prevention Network, NIH's FASTER Trial, and/or other reliable and relevant sources, including new sources that may become available during the course of this postapproval study.

 The sources for the comparison data may include, as appropriate, relevant historical controls such as the CDC's Pregnancy Risk Assessment Monitoring System (PRAMS) and /or other reliable and relevant sources, including new sources that may become available during the course of this postapproval study.

 The sources for the comparison data may include, as appropriate, relevant historical controls such as Surveillance Epidemiology and End Results (SEER), Brinton et al. (2000, 2001) (Brinton, L.A., et al. 2000. Breast cancer following augmentation mammoplasty (United States). *Cancer Causes Control.* 11(9):819-27. *J. Long Term Eff. Med. Implants.* 12(4):271-9; Brinton, L.A., et al. 2001. Cancer risk at sites other than the breast following augmentation mammoplasty. *Ann. Epidemiol.* 11:248-56), Deapen et al. 1997 (Deapen, D.M., et al. 1997. Are breast implants anticarcinogenic? A 14-year follow-up of the Los Angeles study. *Plast. Reconstr. Surg.* 99:1346-1353), and /or other reliable and relevant sources, including new sources that may become available during the course of this postapproval study.

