#### **Exclusion Criteria**

Consistent with the labeling, a woman is not eligible to receive Mentor MemoryGel implants and enroll in the postapproval study if she meets any of the following exclusion criteria:

1. Has active infection anywhere in her body.
2. Has existing breast cancer or pre-cancer of the breast without adequate treatment for those conditions.
3. Is currently pregnant or nursing.

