### **Eligibility Criteria: Saline Breast Implant Control Participants**

#### **Inclusion Criteria**

To be included in the study, each saline control participant must be a woman who:

1. Is a candidate for breast augmentation and is at least 18 years old (primary or revision) **OR** is a candidate for breast reconstruction (primary or revision) with saline breast implants.
2. Signs an Informed Consent Form and an Authorization to Disclose Health Information and Release Medical Records
3. Completes the baseline questionnaire (as evidenced by the participant's signature on the last page of the questionnaire).
4. Agrees to authorize return of the device(s) to Mentor if they are Mentor devices.
5. Agrees via Informed Consent to comply with study follow-up, including full participation in all follow-up questionnaires and responding to questionnaires in their entirety
6. Is a U.S. resident

---

 Breast augmentation includes primary breast augmentation to increase the breast size, as well as revision surgery to correct or improve the result of an original primary breast augmentation surgery.

 Breast reconstruction includes primary reconstruction to replace breast tissue that has been removed due to cancer or trauma or that has failed to develop properly due to a severe breast abnormality. Breast reconstruction includes revision surgery to correct or improve the result of an original primary breast reconstruction surgery.

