#### Complications/Reoperations

The cumulative incidence of key local complications (explantation, and reoperation) for women with MemoryGel implants will be estimated based on physician evaluations for the MemoryGel participants using Kaplan-Meier methodology to estimate the time to the first occurrence of the complication or reoperation. Ninety-five percent confidence intervals will be computed. In addition, the relative frequency of reasons for reoperation will be computed.

Under the original protocol, the purpose of the inclusion of the saline participants was to serve as concurrent controls for assessing rheumatologic and neurologic signs. Rheumatological and neurological data will not be collected under this protocol amendment.

Mentor will generate the following final clinical study reports for submission to FDA:

- One final report at the end of the study phase conducted under Amendment 1, including data from beginning of the study through the end of the study phase under Amendment 1. The statistical analysis will be conducted as described in the original protocol (see below).
- One final report at the end of the study phase conducted under Amendment 2, including data from the execution of Amendment 2 to the end of the study. The statistical analysis will be conducted as described above.

The original analyses conducted to address each of the postapproval study's original objectives are identified below and correspond to issues outlined in Table 1:

*It is important to recognize that this study is observational. As a result, data from this study can be used only to establish association, not causality, and data should be evaluated within the context of the broader composite of literature relating to these issues. All of the analyses, except for the analyses of rheumatological and neurological signs and symptoms, will be based on the MemoryGel participants only.*

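### For the Amendment 1 final report, the breast cancer comparison with national norms pools women reconstructed after treated breast cancer with all other participants, and does not define a new case for them

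*Combined protocol and SAP*

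**What the plan says.** All places are in the combined protocol and SAP.

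- **Cohort.** Section 3.0: "It will include augmentation, reconstruction, and revision patients, each in their naturally occurring proportions at participating study sites". The proportions are not given.
- **Eligibility.** Section 4.0, footnote 2: "Breast reconstruction includes primary reconstruction to replace breast tissue that has been removed due to cancer or trauma". The matching exclusion is "Has existing breast cancer or pre-cancer of the breast without adequate treatment for those conditions", so a woman whose breast cancer has been adequately treated can enrol.
- **Estimator.** Section 11.1, under CTDs, Fibromyalgia, Cancer, Neurological Diseases and Suicide, defines incidence as the "ratio of the number of new cases to the number of person-years of exposure (i.e., observed person-years with silicone breast implants". For the cancer types: "For cancer, the incidences of breast, brain, lung, and other cancers will each be estimated".
- **Analysis set.** Section 11.1: "All of the analyses, except for the analyses of rheumatological and neurological signs and symptoms, will be based on the MemoryGel participants only". Nothing splits the cancer analysis by indication or cancer history.
- **Comparison.** "The relative risk for women with MemoryGel implants as compared to national norms will be estimated", standardised for age, race and any other characteristics judged relevant, with a one-sided 5% test.
- **Comparator sources.** Table 2, footnote 6, lists sources that may be used, among them SEER and augmentation cohorts. One listed title begins "Breast cancer following augmentation mammoplasty (United States". The list is open to other suitable sources.
- **Status.** Amendment 2 stops collecting these data. Section 11.1 still commits the sponsor to a final report on everything through the end of the Amendment 1 phase, analysed by the original protocol's methods, and the cancer comparison is one of these.

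**The concern.** A woman who has had breast cancer is not at risk of a first breast cancer, yet her implant person-years enter the denominator. What enters the numerator depends on a rule that the plan does not give. If recurrences or contralateral cancers count as new, her recorded rate may lie well above the norm. If they do not, or if the breast tissue at risk has been removed, it may lie well below. None of the named comparators is identified as a population reconstructed after cancer.

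The RR would then partly reflect how many such women enrolled and how their later cancers were counted. That could produce a signal with no implant effect, or dilute a real increase among women without prior cancer. More follow-up would not remove this, because it is bias rather than imprecision.

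**Working it through.** **1. The plan's own figure.** Section 11.2 sizes the study for RR 2.0 against 2.85 per 100,000 (scleroderma), one-sided 5%, 80% power.

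- Expected events under the null: 338,000 × 2.85/100,000 = 9.63.
- Exact Poisson test: the critical count is 16, with actual size 3.7% and power 80.2%.
- Person-years per woman: 10 − 0.035 × 55 = 8.075. Then 338,000 / 8.075 = 41,858, against 41,900 stated.

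The figure reproduces. It concerns scleroderma, and the documents state no power or target RR for breast cancer.

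**2. Pooled RR with no implant effect.** Let f be the share of person-years from women with prior breast cancer, and k their recorded breast cancer rate relative to the norm. Take all other women to be at the norm. Then

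pooled RR = (1 − f) × 1 + f × k.

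Neither f nor k is in the documents. I assume f = 5–30% and k = 0.1–5.

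| f | k = 0.1 | k = 0.5 | k = 2 | k = 3 | k = 5 |
|---|---|---|---|---|---|
| 5% | 0.955 | 0.975 | 1.05 | 1.10 | 1.20 |
| 10% | 0.91 | 0.95 | 1.10 | 1.20 | 1.40 |
| 20% | 0.82 | 0.90 | 1.20 | 1.40 | 1.80 |
| 30% | 0.73 | 0.85 | 1.30 | 1.60 | 2.20 |

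The share f is not the reconstruction share. Footnote 2 also counts reconstruction for trauma and for severe breast abnormality. With age standardisation, f is strictly the share of expected cases; the person-year share is used here for simplicity.

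**3. Effect on the test.** Chance that the exact one-sided 5% Poisson test rejects, for an assumed norm of 50 to 200 per 100,000:

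| Person-years | RR 1.00 | RR 1.10 | RR 1.20 |
|---|---|---|---|
| 338,000 (planned) | 4.4–4.8% | 34–81% | 79–99.9% |
| 100,000 (assumed, for lower follow-up) | 4.2–4.4% | 16–38% | 37–84% |

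**4. The other direction.** Suppose the true RR is 1.2 in women without prior cancer, with f = 20% and k = 0.1 (all assumed). The pooled RR is 0.8 × 1.2 + 0.2 × 0.1 = 0.98, and the increase disappears.

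**5. Removing the pooling.** With f = 0 the formula returns 1.00. If the other women themselves differ from the norm, restriction returns their own ratio. It removes the prior-cancer term but does not guarantee that the norm is otherwise comparable.

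**The case against.** The strongest case is that the plan is under-specified rather than wrong.

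- **Adjustment.** A reader might infer that the plan adjusts only for age and race. It does not say that. The clause extends to other relevant characteristics, and prior breast cancer could be one. This stands, but the clause permits a remedy without choosing one. Standardising on cancer history would also need comparator rates by cancer history, and it would not settle what counts as a new case.
- **Comparators.** A reader might infer that SEER and the augmentation cohorts are fixed. They are optional and the list is open. This stands too, but no matched source is named, and one norm does not fit a mixed cohort without stratification. The titles show that the augmentation studies are not reconstruction cohorts. What SEER could supply by cancer history cannot be settled from these documents.
- **New cases.** On an ordinary reading a recurrence is not a new case, so the high values of k rest on a counting rule that the plan never states. That is fair, and it is why the direction is left open. Leaving recurrences out lowers the numerator while the person-years stay in, so the mismatch remains.
- **Association only.** Section 11.1 limits the data to association. That restrains causal language, but the association itself would be shifted by case mix.
- **Scope.** Amendment 2's objectives cover only removal and reoperation. The point therefore concerns one comparison in the Amendment 1 report.

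**Conclusion.** The point holds for the breast cancer comparison in the Amendment 1 final report. It goes beyond missing detail: the stated denominator is all MemoryGel person-years, and it includes women not at risk of a first breast cancer. The documents do not fix the size or the direction. Over the assumed ranges the pooled RR with no implant effect runs from 0.73 to 2.20, and at f = 10% from 0.91 to 1.40, taking all other women to be at the norm.

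Two stronger readings are tempting and are not supported:

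- **The RR will be far from 1, or biased upward.** The assumed k spans 1. Reaching 2.0 needs k = (2 − 0.7)/0.3 = 4.3 at f = 30%, or (2 − 0.9)/0.1 = 11 at f = 10%.
- **The bias should be judged against the RR of 2.0 in Section 11.2.** That target was set for scleroderma, and that sample size is unaffected.

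A large bias is not needed for harm. Under the assumed norms, a spurious RR of 1.1 to 1.2 takes the nominal 5% test to between 34% and 99.9% at the planned person-years, and to between 16% and 84% at 100,000.

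**What to change.** In the analysis plan for the Amendment 1 report:

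1. Make the breast cancer comparison with national norms, numerator and person-years alike, only in women with no breast cancer before implantation.
2. For that comparison, define a new case as a first primary breast cancer.
3. Report recurrences and second cancers in women with prior breast cancer separately and descriptively, without the norm test.
4. Confirm that breast cancer history was recorded at baseline. The baseline questionnaire is not reproduced, and the reoperation form asks only about cancer since the last study visit. If history was not recorded, restrict by indication to augmentation (primary and revision) instead. This also drops women reconstructed for trauma or severe abnormality, and does not by itself prove absence of prior cancer.

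If history or indication is on file, this changes analysis wording and needs no new data. The cost is person-years for this one comparison: of 338,000, an assumed f of 10% leaves 304,200 and 30% leaves 236,600, before any allowance for lower follow-up. The other analyses are unchanged.
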